5.2.1 Inclusion criteria

- Subject (or subject's legally authorized representative) is willing and able to provide written informed consent
- Subject has been implanted with a CRT device for at least 9 months and has had a wireless Medtronic CRT-D device (see Table 4 for Applicable Model Numbers) for at least 34 days
- Subject has >1 year life expectancy
- Subject's CRT-D device has at least 18 months of device longevity left
- Subject has an eGFR > 25 ml/min/1.73 m²
- Subject is NYHA Class II or III
- Subject has elevated BNP values (BNP > 400 or NTpro BNP > 800) within the last 3 months
OR
Subject has had at least one OptiVol threshold crossing in the last 9 months
OR
Subject has had a HF event within the last 9 months

HF event is defined as meeting any one of the following two criteria:

1. Subject was admitted to the hospital for worsening HF
OR
 2. Subject has received Intravenous HF therapy (e.g. IV diuretics/vasodilators) or ultrafiltration at any settings including:
 - Emergency Department
 - Ambulance
 - Observation Unit
 - Urgent Care
 - HF/Cardiology Clinic
 - Patient's Home
- Subjects who are currently prescribed and taking medications for the management of heart failure and are able to tolerate transient increases in diuretic dosage
 - Subject is willing and able to comply with the protocol, including screening, baseline and programming visit(s), remote care directions, follow-up visits, and exit visit.
 - Subject can send device transmissions and daily biometric data with in-home patient devices.

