7.8 Baseline and Programming Visit

Upon successful screening per section 7.7, the subject will return to the site for the baseline and programming visit.

The following information is required to be collected at the baseline and programming visit:

- Demographic Information
- Individualized Medication Intervention Plan (PRN Regimen)
- Baseline Cardiovascular Medication Regimen Information
- HF Event History in the last 6 months
- Safety Parameters Thresholds for PRN Cessation
- OptiVol Information Report from 2090 Programmer
- Device Data (Save to Disk)
- CareLink Transfer Verification

If the threshold value is changed during the study by the sponsor, the subject will be notified and asked to return to the site for a reprogramming visit. Re-programming visits will be performed in the same manner as the initial programming visit.

For information regarding investigational software handling, storage and traceability, refer to section 8.

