13.5.3 Analysis Methods

The number of HF events will be summarized using frequency and percentage, and stratified by the implementation status of Integrated Diagnostic Medication Intervention (1=have ever received the intervention, 0=have never received the intervention). A Poisson regression model will be used to analyze the number of HF events, adjusting for the implementation of

Integrated Diagnostic Medication Intervention. The fit of the Poisson regression model will be checked. If over dispersion is a concern, a negative binomial model may be considered. It is important to note, that those who have received the Integrated Diagnostic Medication Intervention might be sicker when compared to subjects who have never received the Integrated Diagnostic Medication Intervention, and therefore, are more likely to have HF events. Thus, the number of HF events before and after the intervention will be summarized using descriptive statistics for the subjects who have received such intervention.

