7.9.3.2. Endpoint Definition

The endpoint of this objective is the number of HF events per subject, as adjudicated by CEC.

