7.9.3.3. Analysis Methods

The number of HF events will be summarized using frequency and percentage, and stratified by the implementation status of Integrated Diagnostic Medication Intervention (1=have ever received the intervention, 0=have never received the intervention). A Poisson regression model will be used to analyze the number of HF events, adjusting for the implementation of Integrated Diagnostic Medication Intervention. The fit of the Poisson regression model will be checked. If over dispersion is a concern, a negative binomial model may be considered.

PROC GENMOD procedure will be used to perform the Poisson regression analysis:

```
proc genmod data=HEvent;
class PRN;
model HEvent = PRN / dist=poisson link=log;
run;
```

where 'HEvent' is the number of HF events per subject, and 'PRN' refers to the implementation status of Integrated Diagnostic Medication Intervention with 1=have ever received the intervention and 0=have never received the intervention.

It is important to note, that those who have received the Integrated Diagnostic Medication Intervention might be sicker when compared to subjects who have never received the Integrated Diagnostic Medication Intervention, and therefore, are more likely to have HF events. Thus, the number of HF events before and after the intervention will be summarized using descriptive statistics for the subjects who have received such intervention.

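### The HF-event model codes PRN as a fixed ever/never term with no other predictor, so HF events before the first PRN count for the PRN group and the acknowledged severity difference stays in the coefficient

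*SAP*

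**What the plan says.** SAP 7.9.3.2 sets the outcome: "The endpoint of this objective is the number of HF events per subject, as adjudicated by CEC". Each subject contributes one total, not divided at any date.

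SAP 7.9.3.3 gives the model statement, "model HEvent = PRN / dist=poisson link=log", where PRN "refers to the implementation status of Integrated Diagnostic Medication Intervention with 1=have ever received the intervention and 0=have never received the intervention". It contains no baseline covariate, no term that changes over time and no offset for length of follow-up. Protocol 13.5.3 describes the same analysis.

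Both documents name the difficulty. The SAP says that treated subjects "might be sicker when compared to subjects who have never received the Integrated Diagnostic Medication Intervention" and so are more prone to HF events. Two responses follow. If the Poisson fit is overdispersed, a negative binomial model may be used. Separately, HF events before and after the intervention will be described in the subjects who received it. Neither document states a time denominator for that description.

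**The concern.** Exposure is assigned from what happens later. A subject first treated in month 10 carries PRN = 1 from day 0, and any HF event in the first ten months is counted for the PRN group although no PRN had been given. This would happen even if every subject were followed for the same time, so it is distinct from the missing offset.

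The second problem is that PRN is given to subjects whose condition is worsening. A model with PRN alone returns the ratio of two group means. That ratio combines events before treatment, the difference in severity and any effect of PRN. A real benefit could appear as an excess of events. The protocol says that findings will guide a pivotal study, so a reader planning that study could be misled by the ratio.

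**Working it through.** **Inputs from the documents**
- SAP section 6 and Table 1: 43 + 62 + 63 + 40 + 25 = 233 crossings; 233 × 0.45 = 104.85, so 105 PRNs in 200 subjects over 12 months. The plan's figure reproduces.
- Protocol 1.2: follow-up of 12 to about 30 months.

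**Assumptions not in the documents**
- A constant PRN hazard, λ = 105/200 = 0.525 per subject-year.
- An HF-event rate of 0.4 per year, used in the simulations only.
- A gamma frailty shared by PRN and HF events. Its variance is varied, since the documents give no basis for a value.

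**Step 1. Ever-PRN time that precedes the first PRN.** For follow-up t, the mean wait among subjects treated by t is 1/λ − t·e^(−λt)/(1 − e^(−λt)). At t = 1 year this is 1.905 − 0.592/0.408 = 0.456 year, or about 46% of ever-PRN time. With follow-up spread uniformly over 12 to 30 months, it is about 42%.

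**Step 2. Effect of the coding alone.** With no severity gap and equal follow-up, the ever/never ratio is w + (1 − w) × true ratio, where w is the share of time before PRN. For a true ratio of 0.50: 0.456 + 0.544 × 0.50 = 0.73. The HF-event rate cancels.

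**Step 3. Adding a severity gap.** Simulated ever/never ratios, 12 months for every subject:

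| Frailty variance | True ratio 1.0 | True ratio 0.50 |
|---|---|---|
| 0 | 1.00 | 0.73 |
| 0.5 | 1.71 | 1.22 |
| 1.0 | 2.51 | 1.77 |

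A second simulation matched the ever-PRN share implied by the crossing distribution (about 73 of 200 subjects). With no effect it gave 1.33 at a frailty coefficient of variation of 0.5 (variance 0.25) and 2.58 at 1.0. With follow-up of 12 to 30 months, no effect and no severity gap, the missing offset alone moved the ratio to 1.09.

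**Step 4. The before/after summary.** As raw counts, no effect would show an after/before ratio of 0.544/0.456 = 1.19, because treated subjects have more time after than before. As rates within treated subjects, no effect reads about 1.09 and 1.15 at frailty variance 0.5 and 1.0. That is far closer to 1 than the model's 1.71 and 2.51.

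**Step 5. Testing the repair.**
- Splitting records at the first PRN without an offset creates a new error. Rows after PRN average 0.544 year. Rows before PRN or never treated average 0.408 × 0.456 + 0.592 × 1 = 0.778 year. With no effect the count ratio is 0.544/0.778 = 0.70, a false 30% reduction.
- With a log person-time offset and no severity gap, a true 0.50 is recovered (0.51 in simulation).
- With frailty variance 0.5 to 1.0, the split with offset still reads 1.57 to 2.15 under no effect, and 0.78 to 1.07 for a true 0.50.
- Stratifying the split by a simulated nine-month HF history brings a true 0.50 to 0.73 to 0.90. The within-subject before/after rate ratio gives 0.54 to 0.57.

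Adjustment for NYHA class and a subject random effect were not simulated.

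**The case against.** The best defence is that the objective only characterizes how often HF events occur. It has no hypothesis, the study is not meant to show improvement, and a one-term Poisson model just reports two group means. The plan also warns that treated subjects may be sicker and adds the before/after summary for that reason. Expressed as rates, that summary is much less biased than the model. All of this stands and limits the severity. It does not repair the coefficient, which will still be reported, and the negative binomial option alters the variance but neither the exposure coding nor the predictors.

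Two stronger readings are tempting and should not be made.
- A reader might infer that this is the only modelled HF-event result. It is not: the GEE endpoint for Primary Objective 1 requires that no adjudicated HF event occur during the intervention or the following 14 days. Nor does the plan single out this coefficient for the pivotal study.
- A reader might infer that qualifying HF history is lost, because the baseline item is "HF Event History in the last 6 months" while one eligibility route is "Subject has had a HF event within the last 9 months". The documents do not support this. Eligibility verification is collected at screening and covers the nine-month criterion, an HF event is one of three alternative routes, and no planned analysis uses the baseline item as a covariate.

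The numbers also depend on assumptions. The 46% takes the minimum follow-up for every subject; the share falls to about 42% over 12 to 30 months. The frailty range is illustrative.

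**Conclusion.** The point holds as a limited one. The misattribution of events before PRN follows directly from the outcome definition and the coding. Its size, 0.73 for a true 0.50, rests on the plan's PRN rate, a constant hazard, 12 months of follow-up and no severity gap. The severity bias is conceded in principle by the plan, but its size cannot be computed from the documents; 1.7 to 2.5 under no effect is conditional on an assumed frailty variance of 0.5 to 1.0.

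A reader might go further and expect the ratio to become a treatment effect once records are split and adjusted. It would not. Splitting corrects the attribution but leaves most of the severity gap. PRN also follows an acute crossing with High overall risk status, which baseline covariates do not capture.

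**What to change.** In SAP 7.9.3.3:

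1. Split each treated subject's record at the first PRN, coded 0 before and 1 after. Never-treated subjects keep one record coded 0.
2. Use log person-time as an offset, and subject as cluster or random effect.
3. Adjust for baseline HF-event history as already collected, and for NYHA class.
4. Report the before/after summary in treated subjects as events per person-time, with a within-subject rate ratio.
5. State that residual confounding by severity remains, so the coefficient is not a treatment effect.

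Protocol 13.5.3 should be aligned, or the change explained in the study report as Protocol 13.2 allows. The cost is SAP text and code. The first-PRN notification, adverse-event onset dates and exit records are already planned, and Protocol Table 14 already separates events before and after initiation on the day of PRN. No form, visit or aspect of patient care changes.

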7.9.3.4. Determination of Patients/Data for Analysis

All the enrolled subjects who have completed the baseline and programming visit will be included.

7.10. Safety Evaluation

Seriousness and relatedness of adverse events per CEC adjudication will be summarized using counts and percentage. Details of individual adverse events will be listed.

7.11. Changes to Planned Analysis

A screening visit was added after the CIP version 1. This led to an adjustment with the definition of 'enrolled subjects'. In CIP version 1, the study was to enroll 200 subjects assuming they all were eligible for the Integrated Diagnostic Medication Intervention. With CIP version 2 and 3, the study was to enroll 400 subjects where 200 subjects meeting the screening criteria that would proceed towards the baseline and programming visit. So, in the statistical considerations of CIP version 2 and 3, 'enrolled subjects' refers to the enrolled subjects who met screening criteria and completed the baseline and programming visit, i.e. those who were eligible for the Integrated Diagnostic Medication Intervention. This has been spelt out in the SAP.

8. Validation Requirements

At minimum, a Level II validation (i.e. peer review) is required when each study objective is analyzed at the first time (e.g. the first interim analysis). When the same analysis is repeated, the minimum requirement could be a Level III validation (i.e. self review).

9. References

N/A

10. Statistical Appendices

N/A
